#### 7.8.1.5 AEs of special interest (AESI)

The protocol defines the following adverse events that for analysis purposes will be considered as AESIs:

- Decreased renal function
- Hepatic injury
- Metabolic acidosis, ketoacidosis and DKA
- Events involving lower limb amputation

Events of these AESIs are identified through the AE being flagged by the investigator as an AESI on the case report form (CRF).

AE frequency tables will also be created for renal and hepatic events based on narrow SMQs.

Renal: 20000003 Acute renal failure

Hepatic: 20000008 Liver related investigations, signs and symptoms (SMQ)  
20000009 Cholestasis and jaundice of hepatic origin (SMQ)  
20000010 Hepatitis, non-infectious (SMQ)  
20000013 Hepatic failure, fibrosis and cirrhosis and other liver damage-related conditions

#### Metabolic acidosis, ketoacidosis and DKA

The frequency of patients with DKA will be summarised based on the applicable BICMQ at the time of the analysis.

#### Events involving lower limb amputation

The frequency of patients with events involving lower limb amputation will be summarised.

The following specific adverse events will be tabulated by treatment group.

- Genital infections (the applicable BICMQ at the time of the analysis)
- Urinary tract infections (the applicable BICMQ at the time of the analysis)

Specific adverse events of UTIs and genital infections will additionally be summarised by age group, baseline HbA1c, intensity (mild, moderate or severe), whether leading to discontinuation of treatment, time of occurrence (in the first 3 months of treatment or after), duration (<7 days, 7-14 days and >14 days), sex, by how the event was treated (no treatment, therapy assigned, hospitalisation) and the number of episodes per patient. In the number of episodes analysis of UTI and genital infection AEs will be collapsed within each BICMQ regardless of preferred term with the collapsing following the description at the start of

Section 7.8.1 but the condensing will not be conducted in order to maintain multiple episodes per patient.

Kaplan-Meier time to event analyses will also be presented for the UTI and genital infections specific adverse events.

#### Analysis of complicated UTI

Complicated UTI includes serious AEs of narrow BIcMQ UTI, all events of sub-BIcMQ pyelonephritis and all events of preferred term Urosepsis. Frequency of patients with complicated UTI will be summarized.

An additional specific adverse events of volume depletion will be tabulated.

Volume depletion: the applicable BICMQ at the time of the analysis

##### 7.8.1.6 Events qualifying for external adjudication by the Clinical Event Committee (CEC)

An independent external CEC regularly reviews events and evaluates whether pre-specified criteria for these adjudication endpoints are met. Details on composition of the CEC, responsibilities and clinical event definitions are provided in a separate CEC Charter

The CEC will be provided with additional, specified background material on the patients with these events and perform an assessment of the events.

Adjudication assessments will be incorporated to the database. Frequency tables will be provided.

##### 7.8.1.7 Analysis of adjudicated events

Hepatic events will be adjudicated by an external expert committee. The patients with adjudicated hepatic events will be summarized.

##### 7.8.1.8 AEs while patients taking wrong medication

A listing will be provided for AEs that had onset while a patient was taking the wrong medication.

#### **7.8.2 Laboratory data**

For continuous safety laboratory parameters standardised and normalised values will be derived as well as the differences from baseline. The process of standardisation and normalisation as well as standard analyses for safety laboratory data are described in the BI guidance for the Display and Analysis of Laboratory Data [4]. All analyses considering multiple of times upper limit of normal (ULN) will be based on original and not normalised data.

The frequency of the number of patients with AST/ALT elevations  $\geq 3 \times \text{ULN}$ ,  $\geq 5 \times \text{ULN}$ ,  $\geq 10 \times \text{ULN}$ , and  $\geq 20 \times \text{ULN}$  will be displayed.

To support analyses of liver related adverse drug effects, analysis of patients with AST and/or ALT $\geq$ 3xULN with concomitant or subsequent TBILI $\geq$ 2xULN in a 30 day period after AST/ALT elevation will also be performed.

The start of the 30 day time span is triggered by either liver enzyme elevation above the defined thresholds. Patients who fulfil one of the criteria for ALT/AST or total bilirubin elevations above and have no information available for the remaining parameter(s) at the same time-point or within the 30 day time window will not be listed under "ALT and/or AST $\geq$ 3xULN with Total Bilirubin  $\geq$  2xULN".

Patients with elevations as described will be summarised and stratified by Alkaline phosphatase < 2xULN and  $\geq$ 2xULN.

All calculations for the grading of renal function will be based on the originally measured laboratory values given by the laboratory, not on normalised values with BI standard reference ranges. The creatinine clearance and glomerular filtration rate will be estimated according to the two formulas and stored in the trial databases:

- Cockcroft-Gault formula (mL/min):  
$$e\text{Ccr} = (140 - \text{age}) \times (\text{weight in kg}) \times (0.85 \text{ if female}) / (72 \times \text{creatinine (mg/dL)})$$
- Japanese formula (mL/min/1.73m^2):  
$$e\text{GFR} (\text{mL/min/1.73m}^2) = 194 \times [\text{Serum creatinine (mg/dL)}]^{-1.094} \times [\text{age}]^{-0.287} \times [0.739 \text{ if patient is female}]$$

Age will be considered as a discrete variable for the above calculations, and from the same visit.

For the analysis of eGFR and for the covariates in the statistical modelling the values calculated from the above formula using the serum creatinine values from the central laboratory will be used, not the eGFR values provided by the central laboratory. For the assignment of IPVs based on renal function the central laboratory values will be used.

To support analysis of renal function, eGFR throughout the trial will be categorised according to the following eGFR staging.

Table 7.8.2: 1 eGFR staging (by Japanese formula)

Stage	eGFR [mL/min/1.73m^2]	Description
1	$\geq 90$	Normal renal function
2	60 to $< 90$	Mild renal impairment
3	30 to $< 60$	Moderate renal impairment
4	$< 30$	Severe to end-stage renal impairment

Staging of the eCcr will be prepared with respect to the following categorisation and a shift table will be supplied for eCcr as well.

Table 7.8.2: 2 Cockcroft-Gault eCcr staging

Stage	eCcr [mL/min]	Description
1	≥90	Normal renal function
2	60 to <90	Mild renal impairment
3	30 to <60	Moderate renal impairment
4	<30	Severe renal impairment and beyond (e.g., End-stage renal disease)

The analyses of laboratory data will be descriptive in nature and will be based on BI standards (see DM&SM: Display and Analysis of Laboratory Data) [4]

Baseline for safety laboratory parameters will be the last available measurement before the start of randomised study drug. Laboratory measurements taken up to 3 days after the last administration of randomised study drug will be considered as on-treatment.

Laboratory values will be compared to their reference ranges and frequency tables will be provided for the number of patients within and outside the reference range at baseline and the last measurement on treatment. Descriptive statistics will be provided by treatment group for baseline, on-treatment values and for changes from baseline. Frequency tables will summarise the number of patients with potentially clinically significant abnormalities as defined for the new XLAB macro. Summaries will also be presented for patients with elevated liver enzymes. A summary will also be created representing the number of patients per treatment group that experienced a doubling in creatinine on treatment compared to baseline that was out of the normal range.

Only patients with at least one available on-treatment value will be included in the analysis of an individual laboratory parameter. All individual data will be presented in listings.

Urine creatinine does not have a reference range and is determined to calculate the albumin / creatinine ratio. Only the albumin / creatinine ratio will be analysed as for urine creatinine no normalised values can be derived. In cases where urine albumin values are reported to be BLQ (e.g. <3 mg/L) the albumin / creatinine ratio is determined as missing and will not be replaced by estimated values. Four additional summaries will be presented for the descriptive statistics of urine albumin/creatinine ratio by baseline value (normal <30mg/g, microalbuminurea 30-<300 mg/g and macroalbuminurea  $\geq$ 300 mg/g) and transitions from baseline based on the aforementioned categories. Similar analyses will be provided for urine albumin with the following categories (<20mg/L; 20-<200mg/L;  $\geq$ 200mg/L).

A shift table from baseline to last value on treatment for eGFR (Japanese formula) will be provided in Section 15 and a shift table from baseline to last value on treatment for eCcr (Cockcroft-Gault) will be provided in Section 16.1.9.2.

General laboratory evaluation will also be provided for bone markers.

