8. Self-Monitoring Blood Glucose (SMBG) device to be provided at Visit 2 to patients who need wash-out of an OAD or at Visit 4 to patients who do not need washout. Patients should be instructed to monitor fasting blood glucose at least once daily before breakfast (if possible, it is recommended to monitor fasting blood glucose in preprandial state and before bedtime) and at any time the patient is symptomatic related to hypoglycaemia or hyperglycaemia through the entire study period (i.e., after providing the SMBG device until the end of follow-up). In addition, in 3 consecutive days in the week before each scheduled visit, patients will be requested to monitor fasting blood glucose at preprandial state (i.e., before breakfast, lunch and dinner), before bedtime and at any time when the patient is symptomatic. Patients are requested to maintain a diary with daily recordings of glucose values measured by SMBG and of insulin dose through the entire study period.
9. At all the visits which are marked on the [flow chart](#), the respective kit number has to be allocated to the patient via IRT.
10. Only includes liver transaminases (i.e. AST and ALT), ALP, serum creatinine, TSH and urinalysis.
11. No need to be collected in fasted state.
12. In case of early discontinuation from treatment, the end of treatment (EOT) visit has to be performed within 7 days of the last dose of the study drugs. And the follow up (F-up) visit has to be performed after 7 days of the EOT (with +7 days allowance).
13. Patients who are pretreated with insulin alone skip the HbA_{1c} measurement at Visit 4.
14. For patients who completed the trial without any persisting adverse event at EOT, a follow-up visit can be performed as a phone visit (only information on SMBG log, adverse events, and concomitant therapies are to be obtained). For patients who completed the trial with persisting adverse event(s) at EOT and patients who early discontinued the 52 weeks treatment period, an EOT and a follow-up visit (at the follow up-visit, physical examination, vital signs, and safety lab and should be performed additionally) should be performed at clinic visits.
- 15.
16. Only blood sampling for haematology and urinalysis will be performed.
17. C-peptide will be measured at Visit 2 in patients who need wash-out of an OAD or Visit 4 in patients who do not need wash-out.

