3.2 DISCUSSION OF TRIAL DESIGN, INCLUDING THE CHOICE OF CONTROL GROUP

The aim of this study is to evaluate the efficacy and safety of empagliflozin 10 mg and 25 mg in Japanese patients with T2DM whose glycaemic control is insufficient despite diet/exercise and treatment with insulin.

The design of this study is decided according to the draft version of the revised Japanese guideline 'Clinical Evaluation Guidelines for Antihyperglycemic Drugs' [[R15-2907](#)] in which 1-year long-term study is required for any antihyperglycemic investigational product when used as added-on therapy to existing antihyperglycemic drugs which are expected to be co-administered in clinical practice.

Patients who are pre-treated with insulin in combination with 1 OAD will undergo a 10-week wash-out period before a 2-week open-label placebo run-in period. Patients who are pre-treated with insulin alone will skip the wash-out period and proceed to the placebo run-in period.

The 10-week wash-out period will minimise the effect of pre-treated OAD on glycaemic control in patients treated with insulin in combination with the OAD prior to randomisation.

The 2-week open-label placebo run-in period is set to confirm whether the patients fulfil the entry criteria for the double-blind treatment period and to check medical compliance by mimicking the dosing in the double-blind treatment period.

A double-blind and double-dummy design is adopted in order to minimize bias to evaluate the efficacy and safety of two doses (i.e. 10 mg and 25 mg) of empagliflozin and in comparison with placebo, and the 52 weeks of treatment duration is planned in order to investigate the long term efficacy and safety of empagliflozin.

The 1-week follow-up period is considered to be sufficient, as previous studies with empagliflozin have shown that the pharmacodynamic effect of empagliflozin only extends to about 3 days after the last dose and half-life of empagliflozin in Japanese T2DM after 4 weeks of treatment was 12 to 18 hours.

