5.3.3 Safety laboratory parameters

All safety laboratory samples (except at Visit 1) will be collected after a full overnight fast (nothing to eat or drink except water for at least 10 hours) and before investigational drug is taken as described in the [flow chart](#) and [Section 6](#). The blood sample at Visit 1 (screening visit) can be taken with the patient in a fasted or non-fasted state.

All parameters that will be determined during the trial conduct are listed in [Tables 5.3.3: 1](#) and [5.3.3: 2](#). The analysis will be performed by a central laboratory. The respective reference range and details about sample handling and shipment will be provided in the ISF (Lab Manual).

Reduced lab panels are planned for the following visits (For details, see the [flow chart](#)):

- For the screening Visit 1, laboratory only includes liver transaminases (i.e., AST and ALT), alkaline phosphatase, serum creatinine, thyroid stimulation hormone (TSH) , anti-GAD antibody, Ant-IA-2 antibody, FPG, HbA_{1c} and urinalysis.
- C-peptide will be measured at Visit 2 in patients who need washout an OAD or Visit 4 in patients who do not need washout period.
- Free fatty acid (FFA) and Blood ketone bodies will be measured at selected visits. For the details, see the [flow chart](#).
- Bone markers; iPTH (intact parathyroid hormone), 25OH Vitamin D, NTx in urine: planned at Visits 5, 10 and EOT.
- Hematology and urinalysis will also be measured at Visit 6, 7, 9 11, 12, 14, 15, 17 and 18.

Table 5.3.3: 1

Safety laboratory parameters – whole blood, serum or plasma

Haematology

- Haematocrit
- Haemoglobin
 - Reticulocyte count (reflex test if Hb outside normal range)
- Red blood cells (RBC)/Erythrocytes
- White blood cell (WBC)/Leukocytes
- Platelet count/Thrombocytes
- Differential automatic (relative and absolute count):
Neutrophils, eosinophils, basophils, monocytes, lymphocytes

Clinical chemistry

- Albumin
- ALP
- γ -GT (gamma-glutamyl transferase)
- ALT (alanine aminotransaminase, SGPT)
- AST (aspartate aminotransaminase, SGOT)
- Bicarbonate
- Bilirubin total, fractionated if increased
- C-peptide
- Calcium
- Chloride
- Creatinine
- Creatinine kinase (CK)
- hs troponin T (reflex tests if CK is elevated)
- Lactate dehydrogenase (LDH)
- Lipase
- Magnesium
- Phosphate
- Potassium
- Protein total
- Sodium
- TSH (only at Visit 1)
- Urea (BUN)
- Uric acid
- Cholesterol (total)
- HDL cholesterol
- Calculated LDL cholesterol

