5.3.7 Adverse event collection and reporting

AE Collection

The following must be collected and documented on the appropriate eCRF by the Investigator:

- From signing the informed consent onwards through the residual effect period (REP), until individual patient's end of trial:
 - all AEs (serious and non-serious) and all AESIs.
- After the individual patient's end of trial:
the investigator does not need to actively monitor the patient for AEs but should only report relevant SAEs and relevant AESIs of which the investigator may become aware of.

The REP is defined as a period of 7 days after the last trial medication application. All AEs which occurred through the treatment phase and throughout the REP will be considered as on

treatment (see [Section 7.3.4](#)). Events which occurred after the REP will be considered as post treatment events.

AE reporting to sponsor and timelines

The investigator must report SAEs, AESIs, and non-serious AEs which are relevant for the reported SAE or AESI, on the BI SAE form via fax immediately (within 24 hours) to the sponsor's unique entry point (contact details will be provided in the ISF). The same timeline applies if follow-up information becomes available. In specific occasions the investigator could inform the sponsor upfront via telephone. This does not replace the requirement to complete and fax the BI SAE form.

All SAEs and AESIs must be reported immediately to the head of the trial site. With receipt of any further information to these events, a follow-up SAE form has to be provided. For follow-up information the same rules and timeline apply as for initial information.

Information required

For each AE, the investigator should provide the information requested on the appropriate eCRF pages and the BI SAE form, e.g. onset, end date, intensity, treatment required, outcome, seriousness, and action taken with the investigational drugs. The investigator should determine the causal relationship to the trial medication.

The following should also be recorded as an (S)AE in the eCRF and SAE form (if applicable):

- Worsening of the underlying disease or of other pre-existing conditions
- Changes in vital signs, ECG, physical examination and laboratory test results, if they are judged clinically relevant by the Investigator.

If such abnormalities already pre-exist prior trial inclusion they will be considered as baseline conditions.

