## **6.7 BASELINE, TIME WINDOWS AND CALCULATED VISITS**

With regard to efficacy and safety endpoints, the term "baseline" refers to the last observed measurement prior to administration of any randomised study medication.

Measurements taken prior to the first intake of randomised study drug will be considered pre-treatment values. These pre-treatment values will be assigned to a visit according to the nominal visit number as recorded on the electronic case report form (eCRF) or as provided by the laboratory.

The date and clock time of the first drug administration will be used to separate pre-treatment from on-treatment values. Measurements taken after the first intake of randomised study drug will be considered on-treatment values if they have been obtained up to end of the parameter specific follow-up period as defined in [Table 6.7: 1](#) below and will be assigned to the randomised study drug for efficacy analyses, and to the first study drug taken for safety analyses.

Measurements taken after the end of the endpoint specific follow-up period and after the last intake of study drug will be considered post-treatment values.

Table 6.7: 1      Endpoint specific follow-up period for the assignment to active treatment

Endpoint	Last day of assignment to treatment phase (days after study drug stop date)
Efficacy	
HbA 1c	7
Safety	
Adverse events	7
Safety laboratory measurements	3
Pulse rate	1

On-treatment efficacy and safety measurements will be assigned to visits based on time windows around the planned visit dates. These time windows are defined based on the planned number of days after the date of first administration of study drug (usually this is at Visit 5). Reasons to base the time windows on the actual treatment start date rather than the randomisation date are:

- If first intake of study drug shows a large delay by e.g. more than one week after the date of randomisation, a measurement taken four weeks after randomisation rather reflects the drug effect after three weeks than after four weeks and thus may underestimate the treatment effect at this visit.
- With large delays of the introduction of study drug after the randomisation, the time window for the first on-treatment visit could include times the patient was not yet on study drug.

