The time window for the first visit after randomisation starts on the day after the first intake of study drug. This maximises the number of measurements used in by visit analyses and provides consistency with the LOCF approach, but may lead to an underestimation of the treatment effect at the first visit for parameters that react slowly on treatment.

The midpoint between two on-treatment visits defines the end of a time window, with the midpoint being included in the time window of the preceding visit.

The end of the time window of the last on-treatment visit is endpoint dependent (cf. [Table 6.7: 1](#)).

Table 6.7: 2 Time windows for on-treatment efficacy measurement scheduled for each on-treatment visit

Visit number	Visit label	Planned days	Time window (actual days on treatment)	
			Start	End
5	Baseline	0	NA	1 A
6	Week 2	14	2	21
7	Week 4	28	22	42
8	Week 8	56	43	70
9	Week 12	84	71	98
10	Week 16	112	99	126
11	Week 20	140	127	154
12	Week 24	168	155	182
13	Week 28	196	183	210
14	Week 32	224	211	238
15	Week 36	252	239	266
16	Week 40	280	267	294
17	Week 44	308	295	322
18	Week 48	336	323	350
19	Week 52	364	351	Study drug stop date + X B days
End of treatment (EoT) visit	For patients who prematurely discontinue treatment, the end of treatment (EoT) visit should be the last on-treatment visit. That visit will be assigned to a scheduled visit (above) according to the time window it falls into. The time window will end X B days after the study drug stop date.			

A: only values taken prior to the start of treatment with randomised study drug can be considered baseline values.

B: the definition of X is endpoint specific, cf. [Table 6.7: 1](#).

For examinations that are not planned at every on-treatment visit, the time windows will be defined according to the same algorithm, based on the midpoint between the planned visit days of such an examination.

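### End-of-treatment safety chemistry drawn 4 to 7 days after the last dose, which the protocol allows for early discontinuers, drops out of the SAP's on-treatment laboratory summaries

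*SAP*

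**What the plan says.** **Laboratory window.** SAP section 7.8.2 says: "Laboratory measurements taken up to 3 days after the last administration of randomised study drug will be considered as on-treatment". Table 6.7: 1 in SAP section 6.7 gives the same 3 days for safety laboratory measurements. It gives 7 days for HbA1c, 7 for adverse events and 1 for pulse rate. SAP section 6.1 makes clear that these periods are meant to differ by parameter.

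**EOT visit after early discontinuation.** Footnote 12 of the protocol flow chart says that "the end of treatment (EOT) visit has to be performed within 7 days of the last dose of the study drugs".

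**Status of that visit.** SAP Table 6.7: 2 says: "For patients who prematurely discontinue treatment, the end of treatment (EoT) visit should be the last on-treatment visit". The same table row then closes the window a parameter-specific number of days after drug stop, which for laboratory values is 3. The table's title refers to efficacy, but the text of section 6.7 applies the windowing to efficacy and safety measurements alike.

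**Adverse events.** Protocol section 5.3.7 says: "The REP is defined as a period of 7 days after the last trial medication application". SAP section 7.8.1.1 assigns adverse events to treatment over the same 7 days.

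**Chemistry schedule.** Some visits have a reduced panel. Protocol section 5.3.3 says: "Hematology and urinalysis will also be measured at Visit 6, 7, 9 11, 12, 14, 15, 17 and 18". Full post-baseline chemistry is therefore scheduled only at Visits 8, 10, 13, 16 and EOT.

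**Entry to a laboratory analysis.** SAP section 7.8.2 says: "Only patients with at least one available on-treatment value will be included in the analysis of an individual laboratory parameter". It also says that all individual values will be listed.

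**The concern.** The two documents give the same blood sample two different statuses. An EOT sample taken on day 5 after the last dose complies with the protocol and comes from what the SAP calls the last on-treatment visit. Under the 3-day rule it is nevertheless a post-treatment value.

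The gap falls mainly on patients who stop early. Patients attending a scheduled visit are told to take their previous dose about a day before the dose due at that visit (protocol section 4.1.4), so a completer's final sample normally lies well inside 3 days. The 7-day allowance in footnote 12 is written for early discontinuation only.

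Chemistry is sparse between visits, so the EOT sample may be the only liver and renal measurement close to the time of stopping. If it does not count, the last-value tables describe such a patient by a much older sample, or not at all.

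The tables can also disagree. The renal adverse event of special interest (protocol section 5.3.6.1) is a creatinine rise of at least 2-fold that exceeds the upper limit of normal. The creatinine-doubling table in SAP section 7.8.2 uses essentially the same criterion. A doubling first found on day 5 would be an on-treatment event in the adverse event tables and absent from the laboratory table.

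**Working it through.** **1. Size of the gap**
- EOT visit permitted: up to day 7 after the last dose (flow chart, footnote 12).
- Laboratory values counted: up to day 3 (SAP Table 6.7: 1 and section 7.8.2).
- Uncounted permitted days: days 4, 5, 6 and 7, which is 4 of days 1 to 7.

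**2. Age of the last counted chemistry**
- Scheduled full chemistry after baseline: Weeks 8, 16, 28, 40 and 52 (or EOT).
- Intervals: 8 weeks from baseline to Week 8, 16 − 8 = 8, 28 − 16 = 12, 40 − 28 = 12, 52 − 40 = 12.
- If the EOT sample is not counted, the most recent scheduled chemistry can be up to about 12 weeks old.
- Before Week 8 there is no scheduled post-baseline chemistry. A patient who stops then, has EOT on days 4 to 7 and has no unscheduled on-treatment chemistry fails the one-value entry rule for that parameter.
- Haematology and urinalysis are taken at Visits 6 to 18, never more than 4 weeks apart on schedule, so they are much less affected.

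**3. The plan's own figure that uses the 20% loss**
- Protocol section 7.7 needs 100 patients treated with empagliflozin for 1 year: 100 / (1 − 0.20) = 125, or 62.5 per arm. Rounded up, this is 63 per arm and 126 in both arms, as the protocol states.

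**4. Patients who could be affected**
- Inputs: 89 randomised per arm, 267 in total, 20% loss over 52 weeks (protocol section 7.7). The protocol uses the 20% for the empagliflozin arms. Applying it to placebo as well is an assumption.
- Discontinuers: 89 × 0.20 = 17.8 per arm, and 3 × 17.8 = 53.4 in total.
- Affected per arm = 89 × loss × share of EOT visits on days 4 to 7. The documents do not give that share, so it is varied here:

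| Loss | Share on days 4–7 (assumed) | Per arm | Total |
|---|---|---|---|
| 20% | 0 | 0 | 0 |
| 20% | 25% | 4.5 | 13.4 |
| 20% | 4/7 (even spread over days 1–7) | 10.2 | 30.5 |
| 20% | 100% | 17.8 | 53.4 |
| 10% | 4/7 | 5.1 | 15.3 |

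- At 20% loss with even spread, 30.5 / 267 = 11.4% of those randomised.

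**5. With the EOT sample counted to day 7**
- No EOT sample taken within the protocol's allowance falls outside the on-treatment period, so the gap is zero.

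**The case against.** The strongest defence is that the window is deliberate. The SAP sets a separate period for each parameter, and pulse rate has only 1 day. Protocol section 3.2 reports that "the pharmacodynamic effect of empagliflozin only extends to about 3 days after the last dose", and values from days 4 to 7 may therefore be largely off-drug. Counting them could dilute reversible laboratory changes. This stands as a reason not to replace the 3-day window outright. It does not settle the matter, because the SAP gives no reason for 3 days, the protocol offers that sentence to justify the length of follow-up, and Table 6.7: 2 still calls the EoT visit the last on-treatment visit.

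The second defence is that little is lost. This also largely stands:
- The values stay in the listings, and the patient's earlier on-treatment samples stay in the tables.
- Unscheduled samples are assigned to visits (SAP section 6.7), and liver tests are required when hepatic symptoms occur without results (protocol section 5.3.6.1).
- Laboratory-defined hepatic and renal events of special interest are counted to day 7, and hepatic events are also adjudicated.
- SAP section 7.8.2 does not itself limit the AST/ALT threshold counts to on-treatment values. The detailed rules are in sponsor guidance outside the two documents.

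None of this restores the value to the shift tables or the creatinine-doubling count.

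Third, the 20% is a planning allowance that may include patients with no EOT visit, so about 18 per arm is a ceiling at that loss rate. Even spread is also doubtful, since a patient who stops at a scheduled visit would normally have been dosed about a day before.

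**Conclusion.** The mismatch is real and follows from the text alone. EOT chemistry from days 4 to 7 after the last dose, a timing the protocol allows for early discontinuers, leaves the on-treatment shift, creatinine-doubling and descriptive tables. It can also remove a patient who stops before Week 8 from a parameter's analysis.

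How many patients this touches cannot be determined from the documents. At 20% loss the range is 0 to about 18 per arm. About 10 per arm rests on the assumption of even spread over days 1 to 7.

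A reader might infer that the rule biases the laboratory tables towards looking clean, or hides signals in patients who stopped because of harm. The documents do not support that. Protocol section 3.3.4.1 lists many reasons for stopping, nothing shows that stopping or visit timing differs between arms, and events of special interest remain counted to day 7. The laboratory analyses are descriptive. The primary endpoint is not affected, because HbA1c has a 7-day window.

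**What to change.** In SAP Table 6.7: 1 and section 7.8.2, keep the 3-day display and add a second one in which the EOT sample, up to 7 days after the last dose, counts as on-treatment. Apply it to the last-value shift tables, the liver-elevation counts and the creatinine-doubling count. Comparing the two displays shows how many patients per arm change. Reconcile this with the EoT statement in Table 6.7: 2, so that the SAP says explicitly when an early discontinuer's EOT laboratory sample is on-treatment.

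The cost is SAP wording and a few extra tables. No visit or procedure changes. The drawback is that the added display will include some values taken after the drug effect has partly reversed, which is why it should sit beside the 3-day display and not replace it. New antidiabetic treatment should rarely contaminate these samples, because protocol section 3.3.4.1 requires the EOT visit before any such drug is started.
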